1.1 Overall Design

This is a prospective, observational, single arm, post-market study to assess the safety and performance of the PowerPICC family of devices. In the study, only participants who require one of the study devices may be considered for enrollment. The choice of device required for individual participants is left to the discretion of the clinician. Information will be collected on the study participants and devices before, during, and after catheter insertion, while the device is indwelling, and during device removal to assess both safety and performance. Both short- and long-term use of the PowerPICC devices will be assessed as part of the study.

Screening and Enrollment

After screening against inclusion/exclusion criteria, potential participants will be provided with detailed information about the study. If the potential participant, or parent/guardian in the case of those under 18 years of age, provides written informed consent, he/she will be enrolled in the study.

Index Procedure

Choice of the specific PowerPICC type, size, number of lumens, and length required for an individual patient is left to the discretion of the clinician. The device and insertion site will be prepared according to the device specific IFU. The device will be inserted, and catheter tip location will be confirmed according to standard medical practice and according to the device specific IFU. Once proper placement is confirmed, the procedure will be completed, the catheter aspirated and flushed, and secured/stabilized according to the device specific IFU. The insertion site will be dressed according to the IFU and hospital-specific protocols.

Use and Maintenance Procedures

The PowerPICC device will be used for therapy as medically required, according to the Instructions for Use (IFU) and hospital protocol. The device will be maintained (i.e., flushing, fluid locking, cleansing) and the site maintained (i.e., cleansing, dressing) according to the device specific IFU, standard medical practice, and hospital protocols. When the participant is treated in an acute-care setting, the catheter/site will be assessed daily until the device is removed or until they are discharged with the device in place (then treated as an outparticipant). When the participant is treated in an outparticipant setting, the catheter/site will be assessed at each therapy visit until the device is removed, or until 180 days post-insertion (± 14 days), whichever comes first. For the purposes of endpoint calculations, peripherally inserted central catheters (PICCs) remaining in place after 180 days will be considered to have completed therapy.

Device Removal Procedure

The study device will be discontinued/removed when it is deemed medically appropriate by the participant's treating clinician (e.g., no longer needed, no longer functioning). Removal of the device will be performed according to the device specific IFU, standard medical practice, and hospital protocols.

Investigational Sites

Up to 20 sites in the EU will participate in this study. No more than 20% of participants may be enrolled at any one site.

1.2 Sample Size Considerations

The primary safety endpoint of the study is the incidence of venous thrombosis (VT). The expected venous thrombosis rate is about 10% based on literature review. The statistical rationale of the sample size is based on precision of the point estimates of the primary endpoint, as well as the ability to observe rare adverse events or complications.

Assuming the primary endpoint of VT incidence is 10% for a specific type of device, with a sample size of 150, the precision of the point estimate is 4.8% (i.e. the 95% confidence interval is the point estimate plus/minus 4.8%).

Additionally, with a sample size of 150, the probability of observing at least one rare AE/complication with a 1% rate is 78% and the probability of observing at least one rare AE/complication with a 2% rate is 95%.

A sample size of 150 is proposed for each type of device (PowerPICC, PowerPICC SOLO, and PowerGroshong PICC) for a total of 450 participants in the study.

1.3 Interim Analysis

An interim analysis, to assess study progress, will be targeted when 50% of the subjects have completed the study, or sooner, based on reporting requirements. As all analyses are only exploratory and no confirmatory tests are planned no alpha adjustment for the interim analysis is needed.

1.4 Objectives

The primary safety objective is to assess the incidence of symptomatic venous thrombosis (VT) in patients with PowerPICC, PowerPICC SOLO, and PowerGroshong PICC devices (PICCs) used for both short- and long-term venous access.

The primary performance objective is to assess the rate of therapy completion in PICCs used for both short- and long-term therapy.

2 Safety and Performance Variables

2.1 Primary Safety Variable

The primary safety parameter for this study is the incidence of symptomatic VT defined as any new occurrence of symptomatic VT defined by thrombus presence confirmed by ultrasonography or other imaging.

2.2 Primary Performance Variable

The primary performance parameter for this study is the percent of PICCs that remain in place through the required therapy time period (completion of therapy) (success/failure)

2.3 Secondary Safety Variables

The following secondary safety parameters will be analyzed:

Incidence defined as any new occurrence of:

- Phlebitis
- Extravasation
- Local infection
- Catheter-related bloodstream infection
- Accidental dislodgement
- Vessel laceration
- Vessel perforation

2.4 Secondary Performance Variables

The following secondary performance parameters will be analyzed:

- Percent of patent catheters (number of functional catheters through therapy/total number of catheters)
- Percent of placement success in single insertion attempt (placement success defined as single insertion attempt, proper tip location, and patent catheter) (successful placement / total insertions)
- Usability: Ease of insertion - based on a post-insertion survey

2.5 Further Safety Variables

- Adverse events
- Device deficiencies

3 Statistical Analysis Sets

3.1 Enrolled Set

The enrolled set (ES) consists of all participants who sign the ICF.

3.2 Safety Set

The safety set (SAF) consists of all participants who undergo placement of a study device.

3.3 Evaluable Set

The evaluable set (EVS) consists of all participants who undergo successful placement of a study device and receive at least one treatment through it.

3.4 Additional Subgroup Analysis

All analyses will be presented separately for the type of device (PowerPICC, PowerPICC SOLO, and PowerGroshong PICC).

3.5 Assignment of Analysis Sets to Analysis

The evaluable set will be considered the primary analysis set for the primary performance endpoint. Disposition data will be analyzed on the enrolled set. Demographic data and safety analyses are presented using the safety set.

4 Statistical Evaluation

The three types of devices (PowerPICC, PowerPICC SOLO, and PowerGroshong PICC) will be separately tabulated. Total columns will additionally be displayed for all three different types of devices combined.

No inferential assessments will be performed on any analyzed data.

A detailed description of the planned tables, listings and graphs is given in Appendix A (version 5.0).

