### 10.4.2 Performance

The percentage of PICCs that remain in place through the completion of therapy (success) will be calculated by dividing successful cases by the total number of cases (total number of participants completing therapy with single PICC / total number of participants); 95% confidence interval will be calculated.

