4.5.1 Analysis of Primary Performance Variable

The primary performance parameter for this study is the percent of PICCs that remain in place through the required therapy time period (completion of therapy) (success/failure). A success will be defined as follows:

- subjects which still have the study peripherally inserted central line catheter in place
- subjects who did not have the study peripherally inserted central line catheter in place with the reason for peripherally inserted central line catheter removal:
 - “therapy completed / end of useful medical use (catheter stayed in place through the required therapy time)” or
 - “therapy changed or cancelled”.

The percentage of PICCs that remain in place through the completion of therapy (success) will be calculated by dividing successful cases by the total number of devices with non-missing data on success/failure in the evaluable set and displayed using frequency tables. 95% confidence interval will be calculated.

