4.5.2 Analysis of Secondary Performance Variables

Percent of patent catheters

The percent of patent catheters will be calculated by dividing the number of catheters remaining functional through completion of therapy by the total number of catheters with non-missing data on patency in the evaluable set and displayed using frequency tables. 95% confidence intervals will be additionally calculated.

Percent of placement success in single insertion attempt

The percent of placement success in a single insertion attempt will be calculated by dividing the number of catheters that are placed in a single attempt with proper tip location, and catheter patency by the total number of insertions with non-missing data on placement success and number of attempts and displayed using frequency tables. 95% confidence intervals will be additionally calculated. Data will be presented on the safety set.

Usability: Ease of insertion - based on a post-insertion survey

The usability of guidewires/stylets will be analyzed based on a composite score of performance questions administered in a post-insertion survey.

The results of the insertion user questionnaire will be tabulated. For each question, the individual results will be tabulated. Additionally, for all scores, a numerical score will be applied (5 = very easy / strongly agree; 1 = very difficult / strongly disagree) and basic statistics will be additionally presented. Data will be presented on the safety set. Cases where the use of Sherlock TLS or 3CG is documented with "No" and no documentation is available in the ease of insertion data ("empty CRF documentation") for the respective question, will be displayed as "not applicable/not used" for the corresponding question.

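### Therapy completion and patency are tabulated only in the evaluable set, so a catheter placed but lost before first treatment enters neither rate; the likely bias is upward, its size unknown

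*SAP*

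**What the plan says.** SAP 3.3 defines the evaluable set as "all participants who undergo successful placement of a study device and receive at least one treatment through it". SAP 3.2 defines a wider set: "The safety set (SAF) consists of all participants who undergo placement of a study device".

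For therapy completion, SAP 3.5 says "The evaluable set will be considered the primary analysis set for the primary performance endpoint", and SAP 4.5.1 divides by "the total number of devices with non-missing data on success/failure in the evaluable set". For patency, SAP 4.5.2 divides by "the total number of catheters with non-missing data on patency in the evaluable set". Appendix A plans Tables 5.1.1 (completion) and 5.2.1 (patency) on the evaluable set only. No safety-set or enrolled-set version of either is listed.

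Protocol 10.3 defines the same evaluable population but does not assign it to any endpoint. Protocol 10.4.2 gives the completion formula as "total number of participants completing therapy with single PICC / total number of participants", and protocol 10.5 divides patent catheters by all catheters. SAP section 5 (Changes from Protocol) declares one change, the move to denominators with non-missing data. It does not mention the evaluable-set restriction.

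**The concern.** Both conditions for entering the evaluable set are met or missed after the decision to insert a study device. A catheter that is placed and then occludes, dislodges or is removed before anything is given through it has not stayed in place, or stayed functional, through therapy. Under the plan it leaves the denominator instead of counting as a failure. The two percentages then describe catheters that had already survived to first use, while the protocol's formulas read as shares of all participants or all catheters.

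Therapy completion is the primary performance endpoint. In a single-arm study there is no comparator in which the same exclusion would act, so a reader takes the percentage at face value. Without a second figure or a count of exclusions by reason, the reader cannot see how much the conditioning matters.

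**Working it through.** **The plan's own figures.** SAP 1.2 gives a precision of 4.8% for a 10% VT rate with n = 150: 1.96 × √(0.10 × 0.90 / 150) = 0.0480. It gives 78% and 95% for seeing at least one event at rates of 1% and 2%: 1 − 0.99^150 = 77.9% and 1 − 0.98^150 = 95.2%. All three reproduce. They do not bear directly on this point, but 4.8 points is a useful yardstick. The documents state no expected completion rate, patency rate or share of participants outside the evaluable set.

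**Where each kind of case is counted**

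| Case | Completion (5.1.1) and patency (5.2.1) | Placement outputs (3.1, 5.2.2; safety set) |
|---|---|---|
| Placement failed | not counted | counted |
| Placed, lost or non-functional before first treatment | not counted | counted by its placement result; the later loss is not shown |
| Placed, therapy changed or cancelled before first use | not counted, although a completion success by the 4.5.1 rule | counted by its placement result |
| Placed and used | counted | counted |

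The second row is the gap: the loss of such a catheter enters no tabulated performance rate.

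**Size.** Let f be the share of participants outside the evaluable set. Then

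rate(evaluable) − rate(all) = f × [rate(evaluable) − rate(excluded)].

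If every excluded case is a failure, the gap is f × rate(evaluable), or about 0.9 points per 1% excluded at a 90% rate. The table below assumes 150 participants per device type (SAP 1.2), an evaluable-set rate near 90%, and all excluded cases failures. The last two are assumptions.

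| Excluded | Evaluable set | All 150 | Gap (points) |
|---|---|---|---|
| 0 | – | – | 0 |
| 1 | 134/149 = 89.9% | 134/150 = 89.3% | +0.6 |
| 3 | 132/147 = 89.8% | 132/150 = 88.0% | +1.8 |
| 8 | 128/142 = 90.1% | 128/150 = 85.3% | +4.8 |
| 15 | 122/135 = 90.4% | 122/150 = 81.3% | +9.0 |

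With 8 excluded, the Clopper-Pearson intervals are 84.0–94.5% and 78.6–90.6%. Over assumed evaluable-set rates of about 80% to 95%, the gap runs from 0.5 to 9.5 points for 1 to 15 exclusions.

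**Direction.** Keep 8 excluded and 128/142 in the evaluable set, and let some of the 8 be successes. With 4 successes the full rate is 132/150 = 88.0% (gap +2.1). With 7 it is 135/150 = 90.0% (gap +0.1). With all 8 it is 136/150 = 90.7%, and the gap reverses to −0.5. The bias is upward unless the excluded cases succeed at least as often as those retained.

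**The case against.** The strongest defence is that completion and placement are different questions. A catheter never placed cannot remain in place, and the objectives speak of PICCs used for therapy. Placement failure has its own secondary endpoint on the safety set (Table 5.2.2) and a row in Table 3.1. Keeping dwell and placement apart is a defensible estimand. This stands for failed placements, and it is a good reason to keep the evaluable-set tables. It does not cover a catheter that was placed and then lost before use.

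It can also be said that the protocol defines the evaluable population just before its formulas, that its only other population is everyone who signed consent, and that its denominator names no population. The SAP's assignment is therefore a reasonable reading, and a reader who inferred that the SAP overrode an explicit protocol rule would go too far. What stands is narrower: the protocol does not make the assignment, its formulas are written over all participants or catheters, and SAP section 5 is silent on the restriction.

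A reader might infer that the exclusion always flatters the device. SAP 4.5.1 contradicts that, because therapy changed or cancelled before first use is a success by its rule yet falls outside the set. Nor do the documents support a claim that early losses are especially attributable to the device.

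Part of the information is already planned. Table 1.1.1 counts participants in and out of the evaluable set by device type. Listings 3.6 and 3.7 show device success, removal reason and patency for the safety set with an evaluable-set flag. A summarised rate and a tabulated reason for exclusion are missing. Finally, the study is descriptive, with no performance goal, so no pass/fail decision turns on the shift.

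**Conclusion.** The point holds as a reporting gap with a probable upward bias. Completion and patency are conditional on successful placement and first use, no unconditional version is planned, and the restriction is not declared as a change from protocol. The documents do not support calling both rates inflated as a certainty, or calling failed placements hidden.

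The size is unknown. It is zero with no exclusions. Under the stated assumptions (evaluable-set rate near 90%, every excluded case a failure) it is about 0.6 points for 1 and 4.8 points for 8 of 150, the latter equal to the precision the plan quotes for VT. The gap shrinks as the share of successes among the excluded rises. The change is worth making because it is cheap and the listings already call for the data.

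**What to change.** Keep Tables 5.1.1 and 5.2.1 on the evaluable set and add safety-set versions beside them. Which figure leads the text is a matter of preference.

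In the added tables:

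- Code a catheter removed or non-functional before first treatment for a device or complication reason explicitly as a failure. Changing the set alone is not enough: denominators use non-missing data and SAP 4.7 imputes nothing, so an uncoded case would still drop out.
- Classify therapy changed or cancelled before first use by the existing SAP 4.5.1 rule.
- State whether failed placements count as failures here or are reported only in Table 5.2.2.

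Tabulate the number excluded from the evaluable set by reason and device type. List the evaluable-set restriction in SAP section 5 as a change from protocol 10.4.2 and 10.5.

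The cost is two more performance tables, the tabulation of exclusions, a few sentences of SAP text, and a second figure that may be slightly lower. Listings 3.6 and 3.7 already carry the removal reason, device success and patency for the safety set.

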4.1 Dispositions of Participants and Analysis Sets

Disposition of participants and analysis sets

The disposition of participants and analysis sets, participants per center, participants per country, inclusion and exclusion criteria, and the status at study termination will be shown on the enrolled set.

4.2 Demographics and Other Covariates

Demographic data

Demographic data (age (at signing informed consent), gender, race, body height, body weight, body mass index (BMI)) will be tabulated

Medical history

The proportion of participants with

- implantable devices
- past and/or current use of an artificial heart
- past and/or current anatomical abnormalities of the central venous system
- past and/or current use of an atrial fibrillation or other atrial arrhythmias that affects the p-wave
- known ABSENCE of a p-wave
- abnormalities of the arms
- abnormalities of the chest wall
- history of coagulopathy
- history of hypercoagulopathy
- current treatment with anticoagulants
- central venous access devices
- history of lymph node dissection/ lymphedema
- renal impairment
- treatment with cervical collars or halo traction
- history of phlebitis
- history of venous thrombosis

- history of deep vein thrombosis
- history of catheter related bloodstream infection
- any other relevant medical history

will be tabulated.

Further details of medical history and details of other relevant medical history will be listed.

Baseline information

The primary and secondary diagnosis for current admission and the reason for PICC placement as well as the intended access duration will be tabulated.

Demographics and other covariates will be presented for the safety set.

4.3 Catheter insertion, Maintenance and Removal

Catheter insertion

The location of procedure performance (bedside/ interventional radiology) will be tabulated.

The following information regarding catheter insertion will be tabulated:

- Was the catheter tip repositioned?
- What device was placed?
- What guidewire was used to facilitate insertion?
- Where was the catheter placed?
- Which vein was accessed for the procedure?
- Was an assessment of the vessel/catheter ratio done prior to insertion?
- How many insertion attempts were made?
- Was local anaesthesia used?
- Was the catheter length trimmed?
- Was the insertion of the catheter done using tunneling?
- Was a Sherlock TLS used for placement?
- Was a Sherlock 3CG used for placement?
- What method was used to confirm catheter tip positioning?
- What stabilization method was used?
- What dressing type was used?
- Was the catheter inserted as per the instructions for use?
- Was a second implanted line vascular access device present (together with location and type of second device)?

Basic statistics for the duration between start and PICC is secured and the duration between start and tip position confirmation will be displayed. All catheter insertion data will be presented on the safety set.

Use and Maintenance

All information about participant location will be listed.

Removal

The proportion of participants with study PICC still in place, the reason for PICC removal, the proportion of participants with skin condition around the catheter site normal at removal and the specification of abnormal skin condition, and the use of the PICC line during the study period will be tabulated. Removal data will be presented for the evaluable set.

4.4 Safety Analysis

All primary and secondary safety parameters will be analyzed using descriptive methods. For proportions exact two-sided 95% Clopper-Pearson confidence intervals will be calculated where appropriate. All safety analyses will be based on the safety set.

4.4.1 Analysis of Primary Safety Variable

The primary safety endpoint for this study is the incidence of symptomatic VT defined as any new occurrence of symptomatic VT defined by thrombus presence confirmed by ultrasonography or other imaging.

The incidence rate of symptomatic VT will be calculated as the number of participants with symptomatic VT incidence (as ticked on the AE CRF page) divided by the total number of participants with non-missing data on symptomatic VT in the safety set and displayed using frequency tables. 95% confidence interval for the incidence rate will be additionally presented.

4.4.2 Analysis of Secondary Safety Variables

Complications

For each complication listed as a secondary endpoint, the incidence will be calculated by dividing the number of participants experiencing the event by the total number of participants with non-missing data on the corresponding complication in the safety set and displayed using frequency tables. 95% confidence interval for the incidence will be additionally presented.

The following complications will be analyzed:

- Phlebitis (Preferred term (PT): "Catheter site phlebitis" / Lower level term (LLT): "Catheter site phlebitis")
- Extravasation (PT: "Catheter site extravasation" / LLT: "Catheter site extravasation")
- Local infection (as ticked on the adverse event (AE) case report form (CRF) page)
- Catheter-related bloodstream infection (as ticked on the AE CRF page)
- Accidental dislodgement (System organ class (SOC): "Product issues" / PT: "Device dislocation" / LLT: "Catheter dislodgment")
- Vessel laceration (as recorded on the catheter insertion CRF page)
- Vessel perforation (as recorded on the catheter insertion CRF page)

For local infections additionally the number of participants with local infections confirmed according to protocol (presence of pus at the exit site and/or culture confirmed site infection) by type of device and overall will be displayed in a footnote.

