## 3 OBJECTIVES AND ENDPOINTS

Note: Clinical endpoints are gathered from information collected as part of the participants' routine care. No study specific procedures will be performed.

Objectives	Endpoints
Primary Safety	

 
• To assess the incidence of symptomatic venous thrombosis (VT) in patients with PowerPICC, PowerPICC SOLO2, and PowerGroshong PICC devices (PICCs) used for both short- and long-term venous access.
 
	
 
• Incidence defined as any new occurrence of symptomatic VT defined by thrombus presence by ultrasonography or other imaging
 

Primary Performance	
• To assess the rate of therapy completion in PICCs used for both short- and long-term therapy.	• Percent of PICCs that remain in place through the required therapy time period (completion of therapy) (success/failure)
Secondary Safety	
• To assess the incidence of select complications during catheter insertion and while the catheter is in-situ in patients with PICCs used for both short- and long-term venous access.	
 
• Incidence defined as any new occurrence of: 
 
○ Phlebitis – inflammation of the cannulated vessel identified by redness, swelling, warmth, tenderness, and/or cord formation
 
○ Extravasation – accidental infiltration of a vesicant or chemotherapeutic drug into the tissue around the catheter
 
○ Local infection - presence of pus at the exit site and/or culture confirmed site infection
 
○ Catheter-related bloodstream infection - positive blood culture(s) with a microorganism not related to another source (e.g., UTI) OR positive blood culture(s) with microorganism matching catheter tip culture OR blood cultures from peripheral venous puncture and PICC positive with the same microorganism
 
○ Accidental dislodgement – catheter accidentally dislodged the extent to which it requires replacement
 
○ Vessel laceration – a tear in the tissue of the vessel
 
○ Vessel perforation – a hole formed in the vessel
 
 
 

Secondary Performance	

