erythema								
MARSI								
...								
Total								

	Type of Device											
	PowerPICC (N=xxx)			PowerPICC SOLO (N=xxx)			PowerGroshong PICC (N=xxx)			Total (N=xxx)		
	No. of Purposes (N#)	No. of Part. with Purpose (N)	Part. with Purpose (%)	No. of Purposes (N#)	No. of Part. with Purpose (N)	Part. with Purpose (%)	No. of Purposes (N#)	No. of Part. with Purpose (N)	Part. with Purpose (%)	No. of Purposes (N#)	No. of Part. with Purpose (N)	Part. with Purpose (%)
Use of PICC during the study period												
pain management												
limited peripheral access												
...												
Total												

- Listing 3.6: Removal (*)

Safety Set

Variables: Type of device, Participant, Study PICC still in place, Removal date and time, Reason for removal / Specification of other, Skin condition around the catheter site normal, Specification of abnormal skin condition, Specification of other, Use of PICC line during the study period, Specification of other, Device success, Evaluable Set (yes/no)

Note: Type of devices will be displayed as “by-variable” within a subtitle.

- Listing 3.7: Removal: Complications and Performance (*)

Safety Set

Variables: Type of device, Participant, PICC always patent, Experience of: Venous thrombosis, Phlebitis, Extravasation, Local infection, Catheter related bloodstream infection, Evaluable Set (yes/no)

Note: Type of devices will be displayed as “by-variable” within a subtitle.

4 Safety

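### SAP 4.4.2 counts phlebitis and extravasation by one MedDRA term each, which does not implement the protocol's case definitions and is not declared as a change

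*SAP*

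**What the plan says.** Protocol section 3 gives a case definition for each secondary complication. Phlebitis is "inflammation of the cannulated vessel identified by redness, swelling, warmth, tenderness, and/or cord formation". Extravasation is "accidental infiltration of a vesicant or chemotherapeutic drug into the tissue around the catheter".

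SAP 2.3 keeps the lead-in "Incidence defined as any new occurrence of" but then lists only the names of the complications. The operational rule comes in SAP 4.4.2: "Phlebitis (Preferred term (PT): 'Catheter site phlebitis' / Lower level term (LLT): 'Catheter site phlebitis" and "Extravasation (PT: 'Catheter site extravasation' / LLT: 'Catheter site extravasation". Accidental dislodgement is also taken from a coded term. Local infection and catheter-related bloodstream infection are taken from a tick on the AE form, and local infection gets a further safeguard: "For local infections additionally the number of participants with local infections confirmed according to protocol" is to be shown in a footnote.

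Appendix A, Listing 3.7 (removal: complications and performance) prints items for "Experience of: Venous thrombosis, Phlebitis, Extravasation, Local infection, Catheter related bloodstream infection". SAP 4.4.2 does not name these items as a source for Table 4.2.1.1. SAP section 5, Changes from Protocol, declares only the change of denominator to participants with non-missing data.

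**The concern.** These are pre-specified safety endpoints of a post-market study, so the reported incidence should be that of the event the protocol defines. Under SAP 4.4.2, case status depends on how the investigator worded the AE and which term the coder chose. The protocol signs do not enter the rule for phlebitis, and the infused agent does not enter the rule for extravasation.

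Two consequences follow. A participant could be shown with phlebitis in Listing 3.7 and counted as event-free in Table 4.2.1.1, and the SAP has no rule for resolving the difference. The denominator is also unclear: SAP 4.4.2 divides by participants with non-missing data on the complication, and Table 4.2.1.1 has a missing row, but a coded AE term is simply present or absent. The SAP does not say what makes a participant missing for these two endpoints.

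**Working it through.** **Definition against counting rule**

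| Event | Protocol section 3 requires | SAP 4.4.2 counts | Protocol-confirmed count in SAP? |
|---|---|---|---|
| Phlebitis | Inflamed cannulated vessel, shown by listed signs | One PT with the identically named LLT | No |
| Extravasation | Agent is vesicant or chemotherapeutic | One PT with the identically named LLT, any agent | No |
| Accidental dislodgement | Extent such that replacement is needed | One SOC/PT/LLT, no condition on replacement | No |
| Local infection | Pus and/or positive culture at the site | Tick on AE form | Yes, by footnote |

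For phlebitis, an event that satisfies the signs but carries another term is outside the numerator. For extravasation, nothing in the rule removes a leak of an agent outside the protocol definition if it is coded to that term. For dislodgement, the need for replacement is not checked.

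**Would a planned step catch this?** SAP 4.7 has the data review meeting look at missing endpoint data. SAP 4.9 names successful placement and receipt of treatment as minimum agenda items. Neither provides for checking events against their definitions.

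**The plan's own figures (Protocol 10.2, SAP 1.2).** The inputs are n = 150 per device type and event rates of 1% and 2%. The probability of at least one event is 1 − (1 − p)^150.

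- p = 0.01: 1 − 0.99^150 = 77.9% (stated 78%).
- p = 0.02: 1 − 0.98^150 = 95.2% (stated 95%).

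Both figures reproduce. Neither is specific to phlebitis or extravasation, for which the documents give no expected rate.

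**Illustration 1: incomplete capture of phlebitis.** Let s be the assumed share of true cases coded to the single term. The probability of counting at least one is 1 − (1 − s·p)^150.

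| True rate | s = 100% | s = 75% | s = 50% |
|---|---|---|---|
| 1% | 77.9% | 67.7% | 52.9% |
| 2% | 95.2% | 89.6% | 77.9% |

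**Illustration 2: leaks outside the extravasation definition.** Take a true rate of 1% and let such leaks add f percentage points. For f = 0, 1 and 2 the expected counted rate is 1%, 2% and 3%, and the probability of at least one counted case is 77.9%, 95.2% and 99.0%.

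**Sensitivity of a low count.** One event in 150 is 1/150 = 0.67 percentage points. Exact Clopper-Pearson 95% intervals are: 0 events, 0.0% (upper bound 2.4%); 1 event, 0.7% (0.0 to 3.7); 3 events, 2.0% (0.4 to 5.7). A few reclassified cases would move the estimate visibly, although these intervals overlap heavily.

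The values of s, f, the true rates and the event counts are assumptions. The documents supply none of them for these endpoints.

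**The case against.** The strongest reply is that the coded term only retrieves events and does not redefine them. The SAP is based on the protocol, and site staff are trained on the protocol (Protocol 13.2), so investigators can apply the definitions when they report. SAP 4.8 and 4.9 require checks under a data validation plan and resolution of queries. That plan is not among the documents and may include cross-form reconciliation, and the data review agenda is explicitly a minimum. No event leaves the report: all AEs are tabulated by SOC and PT (SAP 4.4.3) and listed in Listing 4.3.1.1, and Listing 3.7 prints the investigator's answers. The endpoints are secondary and descriptive, with no threshold and no inferential assessment.

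Much of this stands, and it limits the point. It does not remove it. An investigator can apply the definition correctly and the event can still be coded to another term, and no training changes the absence of an agent condition in the extraction rule. The general AE tables are not the endpoint table and carry no confidence interval.

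Three stronger readings are tempting but unsupported:

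- A reader might infer that phlebitis is biased downward. Over-coding, such as local skin redness recorded as catheter site phlebitis, would push the other way, and nothing in the documents fixes the net direction.
- A reader might infer that every non-vesicant leak is wrongly counted. The protocol definition also covers chemotherapeutic drugs, so only leaks of agents that are neither are at issue, and how such leaks would be coded is not shown.
- A reader might infer that the tables disregard the removal-form answers. SAP 4.4.2 does not name them as a source, but it does not exclude their use in deciding who has missing data.

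**Conclusion.** The SAP's counting rules for phlebitis and extravasation do not implement the definitions in protocol section 3, and the change is undeclared. This is visible on the face of the documents and needs no assumption. What follows from it is a possibility: protocol-defined phlebitis may be absent from Table 4.2.1.1, and leaks outside the definition may be counted as extravasation. Neither the frequency nor the net direction of misclassification can be derived. The calculations show only that, at the low rates the sample size rationale considers, incomplete capture would erode the stated ability to observe rare complications.

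Because the endpoints are secondary and differently coded events stay traceable in the AE tables and listings, the consequence is limited to the pre-specified estimates and their intervals. The correction is still worth making: the SAP already does the equivalent for local infection, and most of the data needed are already planned for listing.

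**What to change.** In SAP 4.4.2, replace the single-term rule as follows.

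1. Identify candidate cases from a pre-specified list of phlebitis and extravasation terms, plus every yes on the corresponding removal-form items in Listing 3.7.
2. Reconcile the candidates against protocol section 3 at the data reviews before the interim and final analyses. Keep imaging-confirmed symptomatic VT under its own endpoint, so that any thrombophlebitis terms on the list do not blur the two.
3. Use the removal-form item to determine who has non-missing data.
4. Report protocol-confirmed counts in a footnote, as for local infection. For extravasation, do so where the infused agent is recorded or can be obtained by query.
5. Apply the same check to accidental dislodgement, confirming that replacement was needed.
6. Declare the change in SAP section 5.

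The cost is SAP wording and a short review listing built largely from Listings 4.3.1.1 and 3.7. A few cases will need manual review. No visible text shows that the infused agent is collected per event: Protocol 7.4.1 records type of use, and Listing 3.6 records use of the line over the study. Some extravasation cases may therefore need a site query. The reported rates may look slightly less favourable.
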